Discrete Choice. Interdisciplinary research describes choice as a function of the relative expected value of the options at hand.^{61, 62} Further, an option’s anticipated value is derived from the integrated values of its individual attributes.^{63, 64} Widely used in consumer research, discrete choice experiments (DCEs) reveal the extent to which individual product attributes determine choice.⁶⁵ In DCEs, across several trials, participants chose their preferred option from a selection of products, each described as a set of attributes. The products/combinations of attributes presented in each trial are experimentally varied such that the relative importance of each attribute can be discerned using logistic regression. In tobacco regulatory science DCEs have been used

frequently to evaluate general preferences for cigarette and vaping device characteristics.⁶⁶⁻⁶⁹ Here, we will use the DCE method to investigate the contribution of nicotine content and flavor availability to choices between cigarettes and vaping devices.

OBJECTIVES

We are proposing a four condition ETM study to determine if banning NNC is sufficient for encouraging smokers to switch to potentially less harmful products or if the availability of higher nicotine and/or flavored alternative products (specifically e-cigarettes) are needed to achieve maximal reductions in smoking.

METHODS AND MEASURES

Overall Study Design

We propose to conduct a within-subjects, multi-session virtual lab study and validation field assessment to determine how the availability of flavored e-liquids affects product purchasing among cigarette smokers. Adult daily cigarette smokers (N=64) will be recruited for this study. After initial eligibility is assessed, participants will complete six virtual sessions (1 baseline, 4 experimental, and 1 follow-up) and three in person sessions with one field assessment to evaluate their tobacco use.

Design and Setting

Participants will be recruited from Winston-Salem, NC and the surrounding area using advertisements on public transit, community flyers, and social media.. In-person lab visits to drop off biosamples and pickup study products will be conducted at the Wake Forest Tobacco Control Center of Excellence located in Biotech Place in the Innovation Quarter.

Subject Selection Criteria

We anticipate recruiting up to 100 participants to achieve 64 completers.

Inclusion criteria:

1. 21+ years of age

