Participants will undergo one of four marketplace conditions during Virtual Visits 2-5, with the order of administration randomized across participants.

- Marketplace Condition 1 includes moderate nicotine content vape with all flavor e-liquids.
- Marketplace Condition 2 includes moderate nicotine content vape with tobacco e-liquids.
- Marketplace Condition 3 includes low nicotine content vape with all flavor e-liquids.
- Marketplace Condition 4 includes low nicotine content vape with tobacco e-liquids.

Staff will instruct participants to complete the ETM task as if they are purchasing the products from a retailer, and that one iteration of the task will be randomly selected and will determine which products they will use during the field assessment. In reality, we will randomly assign which condition is used (Condition 2 or 4) but will assign products based on when NNC were not available to simulate a nicotine content reduction policy.

For each marketplace condition, participants will complete 7 iterations of the ETM task in ascending order. The prices for NNC cigarettes on the ETM will be set at: \$0.12, \$0.25, \$0.50, \$1.00, \$2.00 per cigarette; in the 1st ETM condition, NNC cigarettes will be set at \$0.25 with no VLNC available to purchase to simulate current market status; while in the 6th ETM condition, NNC will be eliminated from the marketplace to simulate a nicotine content reduction policy. The costs for the other products will reflect average prices in NC and will not change during the task. For each task iteration, participants will receive individually-tailored account balances approximately equal to the money they would spend on cigarettes for seven days. They can purchase as many or few products as their account balance allows. Participants are not required to buy products from the ETM or can buy nicotine gum if they prefer. If they do not buy products from the ETM and do not use tobacco products during the field assessment, then they will receive their ETM account balance at Virtual Visit 6. This payment is delayed to reduce the likelihood that they will use this money to buy their preferred brand cigarettes, thus decreasing the validity of the ETM task.

Participants will be instructed to use only the products purchased from the ETM during the subsequent 7-day period after Virtual Visit 5 and told that we will assess adherence at Lab Visit 3.

In-Person Lab Visit 2

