Participants will be paid \$160 for completing the study. They will earn \$30 for completing Virtual Visit 1, \$15 per visit for completing Virtual Visits 2-5, \$20 for Virtual Visit 6, plus a \$50 bonus for completing the study. Participants who do not meet enrollment criteria at Virtual 1 will earn \$20 for attending the visit. Participants who start but do not complete the study will receive payments for the virtual visits attended. They will not receive the \$50 completion bonus. Participants will also be reimbursed up to \$20 per in-person lab visit for transportation costs.

ANALYSIS PLAN

Primary Outcome

- Number of cigarettes purchased (analyzed as raw data and using derived behavioral economic measures).

Secondary Outcomes

- E-liquid purchased (analyzed as raw data and using derived behavioral economic measures).
- Relative importance and utility data from discrete choice experiment
- Perceived Health Risk Scale scores
- Product Evaluation Scale scores
- Minnesota Nicotine Withdrawal Scale scores
- Questionnaire on Smoking Urges scores
- Tobacco Product Interest scores
- Tobacco Policy Questionnaire scores

Exploratory Outcomes

- Themes emerging from the qualitative interviews
- Product use during Field Assessment
- Biomarkers of exposure during Field Assessment

Sample Size/Estimation/Analysis

Statistical analysis plan

This ETM study will use a 2x2 factorial design. The primary objective will be to evaluate the effect of the two factors – e-liquid nicotine content (moderate vs. low) and e-liquid flavors (all flavors available vs. only tobacco flavor) – on purchasing behavior during virtual visits 2 – 5. Product use behavior, biomarkers of exposure, and other measures of smoking behavior during the field assessment will be evaluated in exploratory analyses.

Analysis of the Primary Outcome

The primary outcome will be the number of cigarettes purchased during the virtual visits. These data will be analyzed both in their raw form (i.e. the raw number of cigarettes purchased) and using derived behavioral economic measures. This is a within-subject design, with each participant providing data under all four factor combinations, and, for the raw data, each participant will provide data for all price combinations nested within a visit.

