Raw data will be analyzed using a linear mixed-effects model that includes main effects for e-liquid nicotine content (low vs. moderate), e-liquid flavors (all vs. tobacco only), visit, price condition (analyzed as a categorical variable), and a carryover effect for the previous visits condition (treated as a four-level categorical variable, and random effects for participant and visit nested within participant. This will account for correlation from multiple observations from the same participant, both within and across visits. We will also evaluate whether there is an interaction between the e-liquid nicotine content and e-liquid flavors factors. If significant, the interaction will be included in the model; otherwise, it will be removed. The analysis of derived behavioral economic measures will follow an analogous approach, except that for each measure, there will only be a single outcome for visit. As a result, our linear mixed-effects model will not include a main effect for price condition, and there will only be a single random effect for each participant. Behavioral economic measures will be derived by generating demand curves using an exponential demand equation. Specific measures considered will include: Alpha - the rate of change in demand, and Q_0 – peak consumption. For all analyses, assessments of key model assumptions will be completed and we will consider transformations or alternate analytic approaches if these assumptions are violated.

Analysis of Secondary Outcomes

The analysis of secondary endpoints will be analogous to the analysis described above for the primary endpoints. The amount of e-liquid purchased will be analyzed both as the raw data for each price condition and using derived behavioral economic measures. The analysis of these endpoints will be completed using linear mixed-effects models with the fixed and random effects terms described above. The analysis of the various scales and scores collected at each visit will follow the same approach as the analysis of derived behavioral economic measures described above. As before, assessments of key model assumptions will be completed and we will consider transformations or alternate analytic approaches if these assumptions are violated.

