For the qualitative data, we will use grounded theory to develop hypotheses related to the topics of interest. Interviews will be audio-recorded and transcribed verbatim. Audio transcriptions will be reviewed for accuracy and entered into Atlas.ti or another qualitative data management software program. Two research staff members will code the first five interviews to achieve greater than 90% interrater reliability and then every 10th interview to ensure integrity. The research team will analyze the interviews using iterative analyses including qualitative research techniques of open and axial coding; major thematic categories; analytical domains; triangulation of data; comparisons within and between groups; and documenting analytical pathways. Saturation will be achieved when no new themes emerge.

[figure not shown]
Missing Data

Study staff will make every effort to minimize missing data in the proposed study. Nevertheless, we plan to complete a sensitivity analysis to evaluate the impact of missing data on trial conclusions. We will compare subjects with and without missing data in order to identify baseline covariates associated with missing data. Our primary approach to handling missing data will be multiple imputation where missing values are imputed using regression models developed from baseline covariates (Little and Rubin, 2002). In addition, we will conduct a sensitivity analysis of the primary and secondary endpoints using a complete-case analysis, baseline-carried-forward and last-observation carried forward. The results of these analyses will be compared to the primary analysis to evaluate the robustness of our conclusions.

Power calculation

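### The primary multiple imputation names only baseline covariates, so read literally it dilutes the nicotine, flavor and interaction effects by the share of marketplace visits missing; the two carry-forward checks do not work for marketplace purchases.

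*Combined protocol and SAP*

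**What the plan says.** All references are to the combined protocol and SAP.

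- **Missing Data.** The primary approach is "multiple imputation where missing values are imputed using regression models developed from baseline covariates". The sensitivity analyses, for primary and secondary endpoints alike, are "complete-case analysis, baseline-carried-forward and last-observation carried forward", and their results are to be compared with the primary analysis to judge robustness.
- **Virtual Visits 2-5.** Each participant meets the four marketplace conditions "with the order of administration randomized across participants". "For each marketplace condition, participants will complete 7 iterations of the ETM task in ascending order", so a missed visit removes all of that condition's purchase records for the participant.
- **Analysis of the Primary Outcome.** The design is within-subject, "with each participant providing data under all four factor combinations". The mixed model has terms for nicotine, flavor, visit, price and "a carryover effect for the previous visits condition". On the nicotine-by-flavor interaction: "If significant, the interaction will be included in the model; otherwise, it will be removed".
- **Subject Selection Criteria.** "We anticipate recruiting up to 100 participants to achieve 64 completers".

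No section says that condition, visit, price or the participant's purchases at other visits enter the imputation. No section says whether participants with only some ETM visits are analyzed.

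**The concern.** An imputation model should contain the terms whose effects the analysis will estimate. Here those terms vary within a participant, and baseline covariates do not. An imputed purchase drawn from baseline covariates alone is therefore the same, on average, whichever marketplace was missed. Mixing such values with real ones pulls every condition contrast toward zero, even when visits are missing purely at random.

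What is at stake is the size of the primary effects. The reported model may also change: other things equal, a diluted interaction is more likely to fail the significance rule and be removed.

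The sensitivity analyses are meant to catch such problems. For ETM purchases, one carry-forward rule has nothing to carry and the other errs in the same direction as the literal primary method.

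**Working it through.** The plan gives no missing-visit rate and no figure for the effect of missing data, so there is no stated result to reproduce. The check does not rest on the plan's power figures. The simulations are illustrative and assume visits are lost at random.

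1. **Condition left out of the imputation.** Let b be a true condition effect and m the share of ETM visits missing, about equal across conditions (reasonable with random order). Observed visits carry b and imputed visits carry 0, so the expected estimate is (1 - m) x b + m x 0 = (1 - m) x b. Pooling rows or imputing visit by visit makes no difference, because random order mixes the conditions evenly within each visit.

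2. **LOCF under dropout.** The carried purchase comes from one of the three other conditions. Of these, one shares the missed visit's nicotine level and two have the opposite level. With levels coded +1 and -1, the average is (1 - 2)/3 = -1/3. The expected ratio is (1 - m) + m x (-1/3) = 1 - (4/3)m. The same count holds for flavor and for the interaction.

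3. **Ceiling for m.** With 100 recruited and 64 completers, at most 100 - 64 = 36 are non-completers. If all 100 are analyzed and each of the 36 misses three of four ETM visits, m = (36 x 3)/(100 x 4) = 108/400 = 27%.

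| m (assumed) | Condition omitted, 1 - m | LOCF, 1 - (4/3)m |
|---|---|---|
| 5% | 0.95 | 0.93 |
| 10% | 0.90 | 0.87 |
| 20% | 0.80 | 0.73 |
| 27% (ceiling) | 0.73 | 0.64 |

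4. **Large-sample simulation.** Inputs: 60,000 participants, random condition order, within-participant correlation 0.4, true effects 0.45, 0.45 and 0.65 (the Power calculation's main-effect and interaction sizes at that correlation), and an assumed baseline covariate explaining 30% of between-participant variance. Whole visits were deleted, either scattered or by dropout. At 5, 10 and 20% missing, the ratios of estimate to truth were:
   - baseline covariates only: 0.94-0.97, 0.89-0.91, 0.79-0.81;
   - condition and interaction added: 0.98-1.02 throughout;
   - LOCF under dropout: 0.93-0.94, 0.86-0.88, 0.72-0.76.

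5. **Imputing condition by condition.** A trial-sized simulation used 64 participants with all four ETM visits plus 9, 18 or 36 who leave after ETM visit 1, 2 or 3. They miss two visits each on average, so m = 18/292, 36/328 and 72/400, that is 6, 11 and 18%. The estimates were 0.98-1.01 of truth, so there is no bias. Variance of the nicotine effect exceeded that of the mixed model on observed records by 3, 5 and 8% at correlation 0.4, and by 19, 39 and 64% at correlation 0.8. The loss arises because the participant's other-visit purchases are ignored. These percentages depend on the assumed variance components.

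6. **Imputing with design terms and earlier purchases.** Using condition, earlier conditions, earlier-visit purchases and the baseline covariate gave 0.99-1.01 of truth, with variance 3-9% above the mixed model. True carryover was set to zero, so the cost of omitting previous condition is not quantified.

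7. **Price.** Leaving price out of the imputation shrinks only the price contrasts. The bias in the condition effects comes from omitting condition.

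8. **Baseline-carried-forward.** The measures listed for Virtual Visit 1 and In-Person Lab Visit 1 include questionnaires and a discrete choice task but no ETM task. The ETM first occurs at Virtual Visit 2, so no baseline purchase exists. Scales collected at those earlier visits, such as withdrawal, urges and perceived risk, do have a baseline value.

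**The case against.** The strongest reply is that the text is brief rather than wrong. An analyst might include condition as a matter of course, or impute within each condition, and either choice removes the bias. That stands: the dilution follows from the literal reading only.

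The second reply is that little may be missing, and this also stands. A reader might infer from 36 non-completers that each misses at least one ETM visit, giving a floor of 36/400 = 9%. The documents do not support that floor. Someone who leaves after Virtual Visit 5, during the field assessment or before the last visits, has complete primary data. Some of the 100 may fail screening, since carbon monoxide and pregnancy testing come only at In-Person Lab Visit 1. If only completers are analyzed, m may be near zero. The 27% ceiling is an extreme case, because the ETM visits are remote and ideally on consecutive days.

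A reader might also want a figure for how often a true interaction would be dropped. None is given here, because such a figure depends on how the imputation is carried out and mixes dilution with the precision lost by ignoring other visits.

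Third, complete-case analysis is already planned. It is not diluted in this way and could expose the problem. That is a real safeguard, but it does not correct the primary estimate or make the carry-forward checks usable.

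**Conclusion.** The point holds in conditional form and should be fixed before analysis; confidence is moderate. If condition is not in the imputation model, the nicotine, flavor and interaction estimates are about (1 - m) of truth. This assumes missingness is roughly balanced over conditions and that partial participants are analyzed. The documents fix no value of m, so the loss may be negligible, and 27% is only an upper limit. It would go too far to say that the plan's primary estimates will be biased, since the text leaves the role of condition open.

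The carry-forward fault does not depend on that reading. For ETM purchases, baseline-carried-forward cannot be carried out, and LOCF inserts purchases from the wrong condition, with effects near 1 - (4/3)m under dropout. Agreement between LOCF and a diluted primary result would therefore not show robustness.

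**What to change.** Either of two changes to the Missing Data section is acceptable:

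- Keep multiple imputation, and state that its model includes nicotine, flavor, their interaction, price iteration, visit, previous condition and the participant's purchases at other visits, as well as baseline covariates.
- Make the mixed model in Analysis of the Primary Outcome, fitted to all observed records, the primary analysis, adding baseline covariates that predict missingness. That model now has none, so switching without adding them would give up information the current plan uses.

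In both cases, drop baseline-carried-forward and LOCF for ETM outcomes and keep complete-case analysis. Baseline-carried-forward may stay for scales measured before the marketplace visits. State whether participants with some but not all ETM visits are analyzed.

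The cost is SAP wording and slightly more modelling work. No study procedure changes.

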Our objective is to enroll 64 completers, and we will test the main effects for e-liquid nicotine content, e-liquid flavors, and the interaction in a within-person design. In a within-person design, the power will depend heavily on the intra-participant correlation, which is unknown *a priori*. To evaluate the power, we simulate our trial under various assumptions regarding the effect size for the main effects and interactions, and the within-participant correlation (see Figure below). For the main effects of e-liquid nicotine content and e-liquid flavor, we have 80% power to detect an effect size of approximately 0.45 with a moderate within-participant correlation of 0.4, which ranges from approximately 0.49 with a within-participant correlation of 0.0, to 0.41 with a within-participant correlation of 0.8. For the interaction, we have 80% power to detect an effect size of

approximately 0.65 with a moderate within-participant correlation of 0.4, which ranges from approximately 0.75 with a within-participant correlation of 0.0, to 0.56 with a within-participant correlation of 0.8.

HUMAN SUBJECTS PROTECTION

Recruitment Methods

Participants will be recruited by posting study information on flyers distributed in the community, Craigslist, social media channels, and Wake Forest Baptist's "BeInvolved" site. Members of the PI's research team will perform recruitment. Coordination of potential participants' virtual visits will be done by phone or by email. Contact information will be stored on password-protected computers that are kept behind locked doors for which only the PI's research team will have access keys and passwords.

Recruitment will be continuous through the course of the study. If necessary, advertisements and recruitment strategies will be redesigned to target specific sub-populations if recruitment falls short of a representative demographic balance.

Participants that have previously performed research with the PI and co-investigator research team and have agreed to be re-contacted for future studies may be contacted for recruitment purposes by email or phone according to their previously stated preference.

Informed Consent

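### The detectable effects in the Power calculation are not reproduced by the planned within-person mixed model; at correlation 0.8 they are too large for its one-outcome-per-visit form

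*Combined protocol and SAP*

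**What the plan says.** The Power calculation section of the combined protocol and SAP rests on simulation with 64 completers. It says that "In a within-person design, the power will depend heavily on the intra-participant correlation", and then gives effects detectable with 80% power.

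- Main effects: "we have 80% power to detect an effect size of approximately 0.45 with a moderate within-participant correlation of 0.4", and this "ranges from approximately 0.49 with a within-participant correlation of 0.0, to 0.41 with a within-participant correlation of 0.8".
- Interaction: 0.65 at a correlation of 0.4, with a range of "approximately 0.75 with a within-participant correlation of 0.0, to 0.56 with a within-participant correlation of 0.8".

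The analysis being powered is under Analysis of the Primary Outcome: "This is a within-subject design, with each participant providing data under all four factor combinations". Raw purchase counts get random effects for participant and for visit within participant. Derived demand measures have one value per visit, so "there will only be a single random effect for each participant". Both models contain visit terms and "a carryover effect for the previous visits condition (treated as a four-level categorical variable". On the interaction: "If significant, the interaction will be included in the model; otherwise, it will be removed".

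The power text does not say which outcome was simulated, nor the alpha, the effect-size scale, the definition of the correlation, the main-effect coding or the handling of the first experimental visit, which has no previous condition. The power plot is missing from the copy reviewed and may give some of these.

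**The concern.** When every participant is seen in all four conditions, both factors and the interaction are within-person contrasts. The participant effect cancels, so raising the correlation should sharply reduce the effect that can be detected. The section says as much, yet its figures hardly move.

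This paragraph is the only quantitative support for N = 64. If its figures do not come from the planned analysis, a reader cannot tell what the trial can detect.

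**Working it through.** **Inputs.** From the plan: N = 64, four conditions per person in random order, 80% power, the model terms above. Assumed: two-sided 0.05 and effects in units of the total SD (variance 1). The multiplier is 1.960 + 0.842 = 2.802.

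**Stated falls, correlation 0 to 0.8.** Main: 1 - 0.41/0.49 = 16.3%. Interaction: 1 - 0.56/0.75 = 25.3%.

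**One outcome per visit, closed form.** Take equal correlation rho and no carryover term. The detectable effect is 2.802 x SE, where SE is:

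- main effect averaged over the other factor: sqrt((1-rho)/64), giving 0.350 / 0.271 / 0.157 at rho 0 / 0.4 / 0.8;
- reference-coded main effect: sqrt(2(1-rho)/64), giving 0.495 / 0.384 / 0.221;
- interaction as a difference of differences: 2 x sqrt((1-rho)/64), giving 0.700 / 0.543 / 0.313.

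Each falls by 1 - sqrt(0.2) = 55.3%. Applied to the plan's own values at rho = 0, the same scaling gives 0.49 x 0.447 = 0.22 and 0.75 x 0.447 = 0.34 at rho = 0.8.

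**Generalised least squares with visit terms, averaged over random orders (rho 0 / 0.4 / 0.8).**

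| Variant | Main, averaged | Main, reference-coded | Interaction | Fall |
|---|---|---|---|---|
| Stated in plan | 0.49 / 0.45 / 0.41 | (coding not stated) | 0.75 / 0.65 / 0.56 | 16%, 25% |
| No carryover term | 0.353 / 0.273 / 0.158 | 0.499 / 0.387 / 0.223 | 0.706 / 0.547 / 0.316 | 55% |
| Carryover, first visit kept | 0.372 / 0.289 / 0.167 | 0.526 / 0.409 / 0.236 | 0.743 / 0.579 / 0.334 | 55% |
| Carryover, first visit dropped | 0.438 / 0.353 / 0.208 | 0.619 / 0.500 / 0.293 | 0.876 / 0.708 / 0.414 | 53% |

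At rho = 0.8 the stated main effect is 0.41/0.293 = 1.4 to 0.41/0.158 = 2.6 times the model value. The stated interaction is 0.56/0.414 = 1.4 to 0.56/0.316 = 1.8 times. At rho 0 and 0.4 the stated values lie above some variants and below others.

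**Power at the stated effects, rho = 0.8.** Power is Phi(d x 2.802/detectable effect - 1.960). The least favourable cases are Phi(0.41 x 2.802/0.293 - 1.960) = 97.5% (98.0% simulated) and Phi(0.56 x 2.802/0.414 - 1.960) = 96.6% (95.3% simulated). The most favourable, 0.41 for an averaged main effect with the first visit kept, exceeds 99.9%.

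**Other assumptions for this model.**

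- Residual-SD units: the rows would be flat.
- Alpha 0.01: the largest values at rho = 0.8 are 0.357 and 0.506, still below 0.41 and 0.56.
- First-order autoregressive correlation: falls of 48-54%; largest values at rho = 0.8 are 0.321 and 0.454.
- Participant-specific effects of constant SD (not in the plan): these add the same amount to the squared detectable effect at every rho. At 0.05 the square must still drop by at least 0.350^2 x 0.8 = 0.098 (main) and 0.700^2 x 0.8 = 0.392 (interaction). The stated drops are 0.49^2 - 0.41^2 = 0.072 and 0.75^2 - 0.56^2 = 0.249.

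**Price-level model.** Let k be the rows per visit (5 to 7, depending on which task iterations are counted), v the visit variance (not given in the plan) and single-row variance 1. In the SEs above, 1 - rho is replaced by the within-person variance of a visit mean.

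- *Rho as between-visit correlation.* That variance is v + (1 - rho - v)/k. A v held constant up to rho = 0.8 cannot exceed 0.2. With v = 0.2, k = 5 and no carryover term, the averaged main effect is 0.350 x sqrt(0.2 + 0.8/5) = 0.210 at rho = 0 and 0.350 x sqrt(0.2) = 0.157 at 0.8, a fall of 25%. With k = 7 the fall is 20%; with the carryover term and the first visit dropped, about 16%. The largest values at rho = 0 (k = 5, first visit dropped) are about 0.37 (main) and 0.53 (interaction), against 0.49 and 0.75. At rho = 0.8 they cannot exceed the visit-level values.
- *Rho as same-visit correlation, with share s due to the visit.* The variance is s x rho + (1 - rho)/k. At rho = 0 it is 1/k, so values are at most about 0.28 and 0.39. It rises with rho once s exceeds 1/k; otherwise it does not rise from that low start. With s of 0.5 to 0.7, reference coding and the first visit dropped, it reaches 0.42-0.50 and 0.60-0.70 at rho = 0.8. The stated rows start higher and fall.

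**The case against.** The strongest reply is that the 53-55% fall belongs to the derived-measure model only. The raw counts come first in the analysis section and carry a visit random effect, and with that term a fall of 15-25% is possible. This stands: a modest fall does not by itself conflict with the raw model. What fails under that reading is the level of the figures when rho is the between-visit correlation and the visit variance is fixed, and their starting level (usually their direction too) when rho is the same-visit correlation.

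It also stands that the stated values at rho = 0.8 are not too large under every reading. With same-visit correlation and a large visit share, the model values can exceed 0.41 and 0.56. Nor are the values at rho = 0 far from the visit-level model with reference coding and the first visit kept (0.526 against 0.49, and 0.743 against 0.75). The missing plot may state the alpha, scale or correlation structure, but none of the readings examined gives both printed rows.

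A reader might infer that the simulation ignored the pairing. Reference-coded main effects tested with a standard error that omits the correlation give 0.495 / 0.462 / 0.413, close to the stated row. The same device gives 0.700 / 0.653 / 0.584 for the interaction, which misses 0.75 and 0.56. The documents do not describe the simulated analysis, so this remains a conjecture.

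**Conclusion.** The concern holds in this form: the six printed figures are not reproduced by the planned within-person mixed model. For one outcome per visit, the detectable effects at rho = 0.8 should be about 0.16-0.30 (main) and 0.32-0.42 (interaction), and the stated 0.41 and 0.56 have about 95% to over 99.9% power. This rests on two-sided 0.05, total-SD units and equal correlation; alpha 0.01 or autoregressive correlation does not remove the gap. For the price-level model the conclusion is narrower: neither reading of rho gives the stated rows under the visit-variance assumptions shown.

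A reader might infer that 64 completers are too few. The documents do not support that. On the visit-level model the error at rho = 0.8 is conservative, and at rho 0 and 0.4 its direction depends on the coding and on the first visit, neither of which the power text fixes. The cause of the discrepancy is unknown.

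**What to change.** Rerun the simulation with the mixed model set out under Analysis of the Primary Outcome, with the within-person correlation carried into the standard errors. State which outcome was simulated (raw or derived), the alpha, the effect-size scale, what the correlation means, the main-effect coding and how the first experimental visit is handled. For the raw outcome, also state the assumed visit variance and the number of rows per visit. Replace the six figures and the plot with the results.

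Keep N = 64. Changing the carryover coding is not part of this fix. The cost is one simulation rerun, one edited paragraph and one redrawn plot, with no change to the visits, sample size or analysis model.
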